1.26 Raltegravir Resistance

The mutations observed in the HIV-1 integrase coding sequence associated with phenotypic resistance to raltegravir include the following amino acid substitutions: at either Q148H/K/R, N155H, or Y143C/H/R) plus one or more additional substitutions. In the raltegravir clinical development program, virologic failure was associated with emergent integrase signature mutations (at amino acids 143, 148, and 155) in 66% of treatment-experienced adults and 44% of treatment-naïve adults failing raltegravir therapy.

In IMPAACT P1066, the emergence of raltegravir-resistant viruses was monitored by isolating viral RNA from all patients displaying virologic failure and determining the

amino acid sequences of the HIV integrase gene, the reverse transcriptase (RT) gene, and the protease inhibitor (PI) gene if the HIV RNA plasma level was >1000 copies/mL, the approximate limit of the resistance assay, and adequate sample was available for testing. In Cohorts I, II, and III (N=126), a total of 27 (21.4%) patients were considered virologic failures by Week 24 and 36 (28.6%) patients were virologic failures by Week 48. Of the 33 Cohort I-III patients for whom genotypic data were available, viruses from 12 (36.4%) displayed signature resistance mutations as follows: 1 at AA 143, 7 at AA 148, and 8 at AA155, which is consistent with observations in adults. In Cohort IV, no patients failed by Week 24 and 4 patients failed by Week 48. No patients in Cohort V met virologic failure criteria by Week 24 or 48. Because of limited blood volume obtained, only 2 of the 4 patients with virologic failure had genotypic data available. One patient had a mutation at AA155 (without other raltegravir associated resistance mutations), and one patient had no known raltegravir mutations detected during study treatment.

1.27 Special Concerns for the Use of Raltegravir in the Neonate

UGT1A1, the enzyme primarily responsible for raltegravir metabolism, is also the only enzyme that contributes to bilirubin glucuronidation in human hepatocytes, and as such is essential for the biliary elimination of bilirubin from the body [48]. Glucuronidation activity is low in fetuses and in the newborn immediately after birth but increases exponentially over the first weeks and months of life. Hepatic UGT activity in liver samples is very low in samples from 2nd trimester fetuses, and increases roughly 10 fold during the 3rd trimester and then another 100-fold during the first 3 months following a full term delivery [49]. The low level of hepatic UGT activity at birth plays a major role in the elevations of bilirubin routinely seen in the newborn, referred to as physiologic jaundice.

In adults, decreased UGT1A1 activity has been shown to result in increased plasma concentrations of both bilirubin and raltegravir. Atazanavir, an HIV protease inhibitor, is also an inhibitor of UGT1A1 and elevation of direct bilirubin is a very common side effect of atazanavir use in HIV infected adults. When raltegravir and atazanavir are co-administered, raltegravir AUC increases on average by 41% and C_{max} by 77% [50]. Similarly, the *UGT1A1* *28/*28 genotype, one of the common genotypes found in individuals with Gilbert's Syndrome, is characterized by a roughly 30% decrease in UGT1A1 activity and increased serum bilirubin concentrations [51, 52]. Following standard dosing with raltegravir, individuals with the *UGT1A1* *28/*28 genotype have on average an increase of 40% in raltegravir AUC and C_{max} and of 90% in trough concentration compared to individuals with wild type *UGT1A1*. Raltegravir elimination $t_{1/2}$ was not prolonged in the *UGT1A1* *28/*28 individuals, suggesting that increased raltegravir bioavailability due to decreased hepatic first pass metabolism may play a major role in the increase in raltegravir plasma concentrations seen in these individuals [53].

Administration of an exogenous drug that is eliminated by glucuronidation poses special risks in the newborn. Low UGT activity that results in decreased elimination of endogenous bilirubin and physiologic jaundice will also result in decreased metabolism

of an exogenous drug whose major elimination pathway is glucuronidation. A neonatal dosing regimen for such a drug extrapolated from older infants or children may result in accumulation of unexpectedly high and potentially toxic plasma drug concentrations [54]. Chloramphenicol, a drug metabolized predominantly by glucuronidation that causes cardiovascular collapse at elevated plasma concentrations, provides the classic example of the harm that may result from using a drug in the newborn without an adequate understanding of its pharmacology in this population. When chloramphenicol was first administered to neonates in the 1950s, the use of neonatal doses extrapolated from those used in older infants and children in ignorance of the low level of neonatal glucuronidation activity led to the accumulation of chloramphenicol to toxic concentrations and the clinical syndrome of fatal cardiovascular collapse known as gray baby syndrome [55]. More recently, elimination of zidovudine, which is also metabolized by hepatic glucuronidation, has been shown to be decreased in neonates, necessitating use of reduced doses during the first months of life in both term and preterm infants [56, 57]. The reduction in neonatal zidovudine glucuronidation was associated not only with reduced clearance but also with higher bioavailability, consistent with decreased first pass metabolism [58].

Another potential risk posed by neonatal administration of a drug metabolized by UGT1A1 is an increase in neonatal bilirubin levels. Since both the drug and bilirubin share the same elimination pathway via UGT1A1 metabolism, the drug may compete with bilirubin for UGT binding sites, leading to a further reduction in bilirubin clearance and an increase in total serum bilirubin. This is unlikely to be a problem for raltegravir, which has a K_m for UGT1A1 of 99 μM and binds much less avidly to UGT than does bilirubin, which has a K_m of 5 μM for UGT1A1 [22]. K_m , the Michaelis constant, is the substrate concentration at which an enzymatic reaction rate is at half its maximum speed. A low K_m value indicates high affinity between substrate and enzyme, while a high K_m value indicates low affinity.

Competition for neonatal albumin binding sites between bilirubin and an exogenous drug may also present a significant risk to the infant. Under normal circumstances, most circulating bilirubin in the newborn is in the unconjugated (indirect) form rather than the glucuronidated (conjugated or direct) form. Unconjugated bilirubin bound by albumin and other plasma proteins is unable to cross the blood-brain barrier. If the concentration of circulating unconjugated bilirubin exceeds the capacity of albumin for bilirubin binding, then the excess bilirubin will be unbound or “free”, with the potential to cross the blood-brain barrier and cause kernicterus [59]. In the newborn when bilirubin concentrations are high, a drug that displaces bilirubin from albumin binding sites may place the infant at increased risk of kernicterus and death, as was the case when sulfisoxazole was first used in premature neonates [60]. However, raltegravir is unlikely to cause a significant problem by displacement of bilirubin from albumin. The typical concentration of albumin in the healthy newborn ranges from about 3.5 to 4.5 g/dL, or 529 to 680 $\mu\text{mol/L}$ [61]. After factoring in raltegravir protein binding of 83%, raltegravir should occupy approximately 2% of albumin under normal physiologic conditions, which should not increase kernicterus risk significantly. By comparison, kernicterus developed in premature infants when sulfisoxazole concentrations exceeded 205 $\mu\text{mol/L}$ [62].

[figure not shown]
[figure not shown]
In vitro evaluation of the effect of raltegravir on bilirubin-albumin binding was performed in pooled neonatal serum using the peroxidase method [59, 61, 62]. Raltegravir had minimal effect on bilirubin-albumin binding at concentrations of 5 and 10 μM , caused a small, but statistically significant, increase in unbound bilirubin at 100 μM and potentially harmful increases at 500 and 1000 μM . The effect of raltegravir on neonatal bilirubin binding is unlikely to be clinically significant unless concentrations exceed typical peak concentrations of 10 μM (4440 ng/mL) by 50–100-fold [63]

Recently a genetic variant in the *SLCO13* gene (rs2117032-C/T) was found to have a strong association with bilirubin levels in neonates [64]. In order to try to identify potential predisposing factors that might be associated with elevated bilirubin levels in the study population, the UGT1A1 and *SLCO1B3* (rs2117032) genetic variant will be evaluated at the end of the study.

Table 9:
Mean (SD) unbound bilirubin concentrations ($\mu\text{g/dL}$) with no additional drug or in presence of varying concentrations of raltegravir or sulfisoxazole.
*Significantly greater than no drug ($p \leq 0.05$)

Total Bilirubin	No Drug	Raltegravir (μM)					Sulfisoxazole (μM)	
		5	10	100	500	1000	500	1000
10.7 mg/dL	3.46	3.39	3.37	3.95	4.87	6.11	6.60	8.64
	(0.25)	(0.22)	(0.18)	(0.30)*	(0.24)*	(0.26)*	(0.25)*	(0.17)*
18.8 mg/dL	7.60	7.80	8.04	8.39	10.28	11.22	10.77	-----
	(0.27)	(0.32)	(0.18)*	(0.71)*	(0.46)*	(0.72)*	(0.36)*	

Figure 2
Mean (SD) unbound bilirubin concentrations ($\mu\text{g}/\text{dL}$) with no additional drug or in presence of varying concentrations of raltegravir or sulfisoxazole.

[figure not shown]
1.28 P1097: Raltegravir Washout PK Results

IMPAACT P1097 is an ongoing multicenter trial to determine the washout PK and safety of *in utero*/intrapartum exposure to RAL in both low birth weight (≤ 2500 grams) and full-term infants born to pregnant women with HIV infection receiving RAL at the FDA approved adult dose of 400 mg twice daily as part of their cART regimen. Cord blood and a single maternal blood sample are collected at delivery. In Version 1, which enrolled full term infants has been completed [65]. In full term infants, blood samples were collected at 1-5, 8-14, 18-24, and 30-36 hours after birth. In version 2, which is currently enrolling low birth weight infants, blood samples are collected at 1-6, 12-24, 36-48, 72-84, and 108-132 hours after birth. RAL concentrations are measured using a validated HPLC-MS-MS method. Infant $t_{1/2}$ is estimated using terminal 2 or 3 concentration-time points for each infant. Safety of *in utero*/intrapartum exposure to RAL has been evaluated in the full-term infants for up to 6 months of age.

In full-term infants, twenty-two mother-infant pairs were enrolled: 59% of the mothers were African American, 36% were Hispanic. Evaluable PK data were obtained from 19 mother-infant pairs (Figure 3). Median (range) ng/mL RAL plasma concentration values were: maternal at delivery: 540 (12-5809); cord blood 957 (24-3974); ratio of cord/maternal blood: 1.48 (0.32-4.33); initial infant plasma: 671 (13-2672); and infant plasma at 30-36 hours: 291 (<10-1402). Median infant apparent $t_{1/2}$ of RAL was 26.6 (9.3-184) hours. Infant washout RAL concentrations initially increased before decreasing in 9 of 19 (47%) evaluable infants. All infants tolerated RAL exposure well with 20 week follow-up evaluations completed with no unexpected adverse events or transmission of HIV infection [66].

Raltegravir readily crosses the placenta. The plasma $t_{1/2}$ of RAL in neonates is highly variable suggesting potential roles for developmental aspects of neonatal UGT1A1 enzyme activity, redistribution and/or enterohepatic recirculation of RAL. Understanding the features of RAL PK in neonates will be critical for development of a neonatal dosing regimen. P1097 version 2 includes LBW infants and is currently enrolling at both sites in the United States and internationally. It is anticipated that LBW infants will have delayed elimination of RAL as UGT1A1 activity is extremely low in this patient population.

Figure 3
P1097 Washout PK Full term infants
RAL Infant Concentration Time Plot (n=19)

1.29 P1110 Cohort 1: Raltegravir Pharmacokinetic Results

P1110 Cohort 1 infants received RAL administered as a single oral dose within 48 hours of birth in addition to standard of care antiretroviral agents (ARVs) for prevention of perinatal transmission, and a second dose administered at 7- 10 days of life. The initial dose was RAL 3 mg/kg and doses were adjusted on a rolling basis. RAL-exposed infants (infants born to mothers receiving RAL prior to and during delivery) were excluded initially but later were allowed to enroll and received a lower initial dose of 1.5 mg/kg.

Sixteen mother-infant pairs enrolled: 10 RAL- naïve infants (born to mothers who did not receive RAL during pregnancy and delivery) and 6 RAL-exposed infants. There were 8 females and 8 males; the median (range) gestational age was 38.7 (37-40) weeks; and the

median birth weight (range) was 3.02 (2.32-4.20) kg. Evaluable PK results were available for 15 of 16 infants. The first 6 RAL naïve infants received 3 mg/kg initial doses. While none of the 6 infants exceeded the C_{max} upper limit, there were 3 out of 6 infants who exceeded the AUC₁₂ upper limit of 28 mg*h/L. The initial dose was reduced after interim analysis and for subsequent enrollments RAL-naïve infants received a 2 mg/kg dose while RAL-exposed infants received a 1.5 mg/kg for the initial dose. All infants, regardless of maternal RAL usage, received 3 mg/kg for the second dose at 7-10 days of life.

P1110 Cohort 1 (RAL-naïve): Raltegravir Pharmacokinetic Preliminary Results

PK results from Cohort 1 [67-69] were combined with that from older infants and children receiving daily dosing in a population PK model and simulations performed to develop a daily RAL dosing regimen to be evaluated in 20 infants in Cohort 2 [70-72]. The RAL dosing regimen studied in Cohort 2 for infants unexposed to RAL in utero is: 1.5 mg/kg daily starting within 48 hours of life through day 7; 3 mg/kg twice daily on days 8-28 of life; 6 mg/kg twice daily after 4 weeks of age [71, 72].

PK results and 6 week safety data were presented for the first 10 RAL-naïve infants who received the dose under study: 1.5 mg/kg daily through day 7; 3 mg/kg twice daily on days 8-28 of life; 6 mg/kg twice daily after 4 weeks of age [69, 73, 74]. After the first dose of 1.5 mg/kg, geometric mean RAL AUC₂₄ was 38.9 mgxh/L (range 18.6-78.3 mgxh/L). On 3 mg/kg twice daily the geometric mean for RAL AUC₁₂ was 12.1 mgxh/L (range 4.7-24.5 mgxh/L) and C_{min} estimated to be 120.4 ng/mL. Sparse sampling confirmed that RAL plasma concentrations were within the expected range.

There have been no safety concerns associated with daily RAL administration based on safety data through 6 weeks of life. Daily RAL has been well tolerated in the infants receiving this regimen during the first 6 weeks of life. The PK targets and the safety guidelines have been met for the RAL-naïve infants in cohort 2.

2.0 STUDY OBJECTIVES

2.1 Primary Objectives

- 2.11 To evaluate the safety and tolerability through 6 weeks of life of raltegravir oral granules for suspension when administered during the first 6 weeks of life with standard PMTCT ARV prophylaxis to infants exposed to HIV-1 assessed at risk of infection.
- 2.12 To evaluate the pharmacokinetics of raltegravir oral granules for suspension during the first 6 weeks of life along with standard PMTCT ARV prophylaxis.
- 2.13 To determine an appropriate dose of raltegravir oral granules for suspension for use in neonates and infants during the first 6 weeks of life.

2.2 Secondary Objectives

- 2.21 To assess safety and tolerability of raltegravir oral granules for suspension through 24 weeks of life when administered during the first 6 weeks of life with standard PMTCT ARV prophylaxis to infants exposed to HIV-1 assessed at risk of infection.
- 2.22 To investigate the relationship between neonatal raltegravir elimination and UGT1A1 genotype and whether there is an association of UGT1A1 (*28/*28) and SLC01B3 (rs2117032-C/T) with hyperbilirubinemia.

[figure not shown]
3.0 STUDY DESIGN

This is a Phase I multi-center, open label, non-comparative study to evaluate the safety and pharmacokinetics (PK) of raltegravir (RAL) administered to HIV-1-exposed neonates at risk of acquiring HIV-1 infection. The goal is to determine the appropriate dosing regimen of RAL oral granules for suspension that can be safely administered to neonates and infants in the first 6 weeks of life.

The study will enroll approximately 50 mother-infant pairs in order to accrue a minimum of 32 PK evaluable HIV-1-exposed infants.

Mother-infant pairs will enroll at the time of delivery/birth (up to 48 hours of life under protocol Version 1.0 and up to 60 hours of life under protocol Version 2.0). Pregnant women who are expected to have a full term uncomplicated delivery will be identified prior to delivery. The informed consent process will typically be conducted during the 2nd or 3rd trimester; however, the consent process may be conducted in whole or in part after infant birth. Women will be followed until discharge from the labor and delivery unit. Infants will be followed on study for 24 weeks after birth.

P1110 Study Design Schema

Cohort 1:

A minimum of 12 neonates will be enrolled into Cohort 1 to provide data for 12 PK evaluable neonates. All neonates enrolled in Cohort 1 will receive RAL 2 mg/kg as oral granules for suspension administered as single dose within 48 hours of birth, in addition to standard of care ARV for PMTCT prophylaxis, and a second dose administered at 7 to 10 days of life.

The primary purpose of Cohort 1 is generation of PK data that will help inform RAL dose selection for Cohort 2. As this is the first time neonates will be actively dosed with RAL, the extent to which PK may differ from older infants with respect to absorption and metabolism is unknown. The first dose (<48 hours) will provide PK data when infant glucuronidation is known to be at its nadir, and the second dose (7-10 days) will provide information about changes in metabolism in Week 2. The 2 mg/kg single starting dose of RAL is 25% of the total daily dose (6 mg/kg BID) that was studied in infants with HIV infection 4 weeks to < 6 months of age in IMPAACT P1066. Since RAL clearance is substantially lower in the first days of life, based on interim data from IMPAACT P1097, the 3 mg/kg single dose was selected as a conservative first dose to minimize potential safety concerns and still provide informative PK data.

RAL dosing in Cohort 1 may be modified in the range of 1.5 mg/kg to 6 mg/kg per dose. The PK results and safety will be assessed through regular team monitoring (done at least every 4 weeks) and at full cohort accrual to ensure that the individual RAL concentrations are in the target range (not exceeding C_{max} of 19.63 μM and not exceeding an AUC₁₂ of 63.05 $\mu\text{M}\cdot\text{hr}$) and that there

are no life-threatening toxicities probably or definitely related to RAL administration. Based on team assessment of the PK data and review of safety information, the dose may be modified within the stated range for the subsequent participants entering into Cohort 1.

All Cohort 1 infants will have a history, physical examination, and hematology and chemistry laboratory evaluations performed at the time of dosing for each of the two doses, and follow-up visits at 2 weeks, 6 weeks and 24 weeks of life.

Pharmacokinetic sampling for infants in Cohort 1 will include the following:

Dose 1 (within 48 hours of birth) Intensive PK: Pre-dose, 1-2 hours post-dose, 4-8 hours post-dose, 12 (± 1) hours post-dose, and 24 (± 1) hours post-dose.

Day 3-4 Single Random PK: One random PK sample will be obtained with laboratory evaluations on Day 3-4 of life.

Dose 2 (7-10 days of life) Limited PK: Pre-dose, 1-2 hours post-dose and 24 (± 1) hours post-dose.

*Note: For the 12 and 24 hour PK sampling time points, it is necessary to collect blood samples within the window of ± 1 hour for the accurate calculations of PK parameters of raltegravir. However, in the event that a sample collection in this window is not possible, the sample should be obtained within ± 2 hours and this deviation from the sampling instructions should be recorded.

Cohort 2:

A minimum of 20 evaluable infants will be enrolled into Cohort 2 to receive raltegravir for 6 weeks in addition to standard of care ARV for PMTCT prophylaxis. Cohort 2 dosing has been determined based upon modeling and simulation analyses, which included data generated from IMPAACT P1097, P1066 (Cohorts IV and V), P1026s, and P1110 Cohort 1 and incorporated information about UGT1A1 ontogeny to inform the development of neonate metabolic pathways. RAL-naïve infants in Cohort 2 will receive RAL at a dose of 1.5 mg/kg daily as oral granules for suspension starting within 48 hours of birth. RAL-exposed infants in Cohort 2 will receive RAL at a dose of 1.5 mg/kg daily as oral granules for suspension starting within 12 to 60 hours of birth. Additionally, RAL dosing in Cohort 2 may be modified based on ongoing interim analysis of pharmacokinetic data and safety information.

All Cohort 2 infants will have a history, physical examination, and hematology (except for the After Second Dose visit) and chemistry laboratory evaluations performed at all study visits. Additional repeat total and direct bilirubin will be done on day 2-4 of life (after the second dose). Follow-up visits will occur at Day 6-9, Day 15-18, Day 28-32, and 5-6 weeks, 8-10 weeks and 24 weeks of life.

Note: Cohort 1 (RAL-exposed and RAL-naïve groups) and Cohort 2 (RAL-naïve group) were fully enrolled under protocol Version 1.0 and the results of Cohort 1 were used to inform the dosing regimen for Cohort 2, see protocol Section 1.29 for a summary of these results.

Pharmacokinetic sampling for infants in Cohort 2 will include the following:

*Note: PK sampling will ideally be scheduled after RAL has reached steady state (approximately 7-10 days after the dose increase). For example, the Day 15-18 PK sampling collection visit should ideally be scheduled 7-10 days after the infant received his/her RAL dose regimen increased from 1.5 mg/kg once daily to 3 mg/kg twice daily.

Entry with first dose: within 1 hour pre-dose, and 1-2 hours, 6-10 hours, 20-24 hours post-dose.

After second dose: PK sample obtained 3-6 hours post-dose with laboratory evaluations.

Day 6-9 of life: within 1 hour pre-dose of initiating 3mg/kg twice daily. A physical exam will also be conducted at this visit.

Day 15-18 of life: within 1 hour pre-dose, and 1-2 hours post-dose, 4-6 hours post-dose, and 8-12 hours post-dose.

Day 28-32 of life: within 1-hour pre-dose of initiating 6 mg/kg twice daily.

Week 5-6 of life (33-42 Days of life): within 1 hour pre-dose, and 3-6 hours post-dose.

See Section 6.21 for Cohort 1 and Cohort 2 PK target exposures.

3.1 Evidence of HIV infection and resistance testing (Cohorts 1 and 2):

All infants will receive appropriate testing for evidence of HIV-1 infection within 60 hours of birth (if not done as per standard of care), and at 6 and 24 weeks of life. If any study participant is found to be HIV-1 infected during the course of the study, blood samples for viral resistance testing to raltegravir and ARVs will be collected as soon as possible after confirmation of vertical transmission. Infants who become HIV infected will have hematology, chemistry, lymphocyte subsets, and HIV viral load laboratory evaluations performed every 3 months up to 24 weeks of life.

3.2 Optional genotyping (Cohorts 1 and 2):

Optional genotyping for UGT1A1 and SLCO1B1 polymorphisms will be performed in infants undergoing PK sampling to determine how polymorphisms, such as UGT1A1*28/*28 genotype, associated with decreased UGT1A1 activity impact RAL elimination in the neonate. UGT1A1 activity is reduced in all neonates at birth but increases rapidly over the first weeks of life, and the effect of UGT1A1 polymorphisms on the metabolism of RAL during this period of time is unknown.

3.3 Raltegravir Compassionate Use (Cohorts 1 and 2):

Raltegravir will be provided to infants through the protocol for the duration of the study as part of combination antiretroviral therapy (cART), but the choice of the ARV regimen will be left to the discretion of the site investigator. At the end of the study, infants with HIV infection who are receiving the RAL granules as part of their cART regimen at sites where the RAL granules are either 1) not commercially available in that country for the caregiver to purchase, or 2) the caregiver cannot gain access to the granules via a government program, then Merck will arrange for access to the granules through the local Merck subsidiary at no cost to the patient.

See Appendix I, Maternal Schedule of Evaluations, Appendix II-A, Infant Schedule of evaluations for Cohort 1, Appendix II-B, Infant Schedule of Evaluations for Cohort 2, and Appendix II-C, Schedule of Evaluations for Infants Who Become HIV Infected, for a complete description of the procedures to be performed.

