8.2 Outcome Measures

(Outcome Measures are for infants only; maternal data are to be used as covariates, not as outcomes)

8.21 Primary Endpoints for Cohorts 1 and 2

Toxicity Endpoints: Toxicity from study entry through 6 weeks of life

- Adverse events of Grade 3 or 4 severity or death (primary safety endpoint for final analysis)
- Suspected adverse drug reaction (SADR) of Grade 3 or 4 severity or death (primary safety endpoint for dose finding guidelines described in Section 8.52) but secondary safety endpoint for the analyses described in Section 8.71)

Pharmacokinetic Endpoints: (See Section 9.0: Clinical Pharmacology Plan)

8.22 Primary Response Variables for Cohorts 1 and 2 Pharmacokinetic parameters (See Section 9.0)

8.23 Secondary toxicity endpoints for Cohorts 1 and 2: Toxicity from study entry weeks through 24 weeks of age

- Adverse events of Grade 3 or 4 severity or death
- Suspected adverse drug reaction (SADR) of Grade 3 or 4 severity or death

8.24 Secondary Response Variables for Cohorts 1 and 2

- UGT1A1 genotype (presence or absence of *28/*28 genetic variant)
- SLCO1B3 (rs2117032-C/T) genotype
- Hyperbilirubinemia defined as total bilirubin exceeding 16.0 mg/dL or infant receiving phototherapy, or transfusion therapy, or other therapies for hyperbilirubinemia

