To assess the safety and tolerability of RAL through 24 weeks of life, descriptive statistics will be calculated summarizing the proportion of infants who had an adverse event of Grade 3 or 4 severity or death based on safety data from study entry through 24 weeks of age on all safety evaluable infants in each of the four study groups. A similar analysis will be done to summarize proportion of infants who had an SADR of Grade 3 or 4 severity or death.

To investigate the relationship between neonatal raltegravir elimination and UGT1A-1 genotype, participants will be divided into subgroups, based on whether or not they exhibit polymorphisms on UGT1A-1. Descriptive analyses will be performed to compare these subgroups with respect to measures of central tendency and dispersion for raltegravir AUC.

Similar descriptive analyses will also be performed to investigate the association of UGT1A1 (*28/*28) and SLCO1B3 (rs2117032-C/T) with hyperbilirubinemia. If the sample size and the data distributions make this possible, a logistic regression model predicting for probability of neonatal hyperbilirubinemia with UGT1A1 (*28/*28) genotype, SLCO1B3 (rs2117032-C/T) genotype, gestational age and gender as predictors will be fitted on the pooled data across the two cohorts. Note that the sample size may be too small and/or there may be insufficient cases of hyperbilirubinemia to make this possible. If this analysis can be done, it will have minimal power, but the size and directionality of effects will be compared with those predicted on the basis of previous findings.

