APPENDIX II-B - FOOTNOTES FOR INFANT SCHEDULE OF EVALUATIONS
FOR COHORT 2

1. History includes all non-protocol laboratory tests, HIV test results, antiretroviral agents (for PMTCT), concomitant medications, and any intercurrent illnesses since last visit.
2. Physical examination includes infant Apgar score, birth weight and length, gestational age, gender, and ethnicity.
3. Complete physical examination includes temperature, blood pressure, heart rate, respiratory rate, weight, length, and head circumference.
4. Pre and post-dose monitoring includes a telephone call by study staff to review medication instructions and check any side effects. Clinic staff will call the participant's home prior to PK sampling days to confirm adherence, understanding of dosing, and no intercurrent illnesses that might preclude PK sampling. If correct doing for 48 hours prior to PK sampling is not confirmed, PK sampling will be rescheduled. Post PK sampling visit days, study staff will review for adverse events and answer any questions for participants' parents by phone. If adverse events are noted, early return visits to clinic may be arranged.
5. Hematology includes CBC (complete blood count) with differential and platelet count which may be obtained any time on the first day of life.
6. Chemistries include AST, ALT, creatinine, and total and direct bilirubin which must be obtained prior to enrollment of the infant.
7. Only total and direct bilirubin required.
8. HIV NAT may be either HIV RNA or HIV DNA. Collect 1-3mL depending on the type of platform performed at the site.
9. Obtain HIV NAT at entry if NOT done as part of standard of care.
10. Participants with confirmed vertical transmission should have 2mL of blood drawn for viral resistance testing to raltegravir and other ARVs as soon as possible after confirmation of HIV infection and should have safety assessments as described in Appendix II-C.
11. Genotyping (optional) for UGT1A1 and SLCO1B1 polymorphisms will be done using dried blood spot on filter paper which may be obtained with any blood sample.
12. Collect PK samples at time points as specified in Section 3.0.
13. Acceptable methods of blood collection for PK samples and laboratory evaluations are by venipuncture, heel stick or indwelling line.
14. When possible, an assessment of infant feeding (type and time of last infant feeding prior to RAL dose) should be recorded.

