Note: This table is for Cohort 2 RAL-naïve group only and should we have data on Cohort 2 RAL-exposed group, additional columns for: (i) RAL-exposed group, and (ii) Overall Cohort 2, will be added. Formal comparisons for all Cohort 2 infants will be done by then.

Table: Association between UGT1A-1 genotypes and hyperbilirubinemia (yes/no) with Fisher’s Exact Test.

Table 10: Summary of Cohort 1 Infant Hyperbilirubinemia between UGT1A1 Genotype Groups (mock-up table)

Characteristic		Wild-type	Mutation				Overall (N=0)	P-value* for all genotype groups	P-value* for Wild-type vs. Mutation
		(TA)6(TA)6	(TA)5(TA)6	(TA)6(TA)7	(TA)7(TA)7	Overall			
Hyperbilirubinemia	Yes	0	0	0	0	0	0.000	0.000	
	No	0	0	0	0	0			

*Fisher’s Exact Test. The power of test will depend upon the distributions of the variables to be analyzed, but will be extremely limited due to the small sample size.
Note: Similar table will be created for Cohort 2 infants.

Table: Association between SLCO1B3 genotypes and hyperbilirubinemia (yes/no) with Fisher’s Exact Test.

Table 11: Summary of Cohort 1 Infant Hyperbilirubinemia among SLCO1B3 Genotype Groups (mock-up table)

Characteristic		C/C (N=0)	C/T (N=0)	T/T (N=0)	Total (N=0)	P-Value*
Hyperbilirubinemia	Yes	0	0	0	0	0.000
	No	0	0	0	0	

*Fisher’s Exact Test. The power of test will depend upon the distributions of the variables to be analyzed, but will be extremely limited due to the small sample size.
Note: Similar table will be created for Cohort 2 infants.

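### The protocol contradicts itself on which transporter gene is typed: SLCO1B1 where genotyping is ordered, SLCO1B3 (rs2117032) where the result is used

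*Protocol*

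**What the plan says.** Three places in the protocol say what is to be genotyped. Section 3.2 reads "Optional genotyping for UGT1A1 and SLCO1B1 polymorphisms will be performed in infants undergoing PK sampling". Footnote 11 of the Cohort 2 schedule (Appendix II-B) reads "Genotyping (optional) for UGT1A1 and SLCO1B1 polymorphisms will be done using dried blood spot on filter paper which may be obtained with any blood sample", and footnote 11 of the Cohort 1 schedule (Appendix II-A) names the same genes and specimen. The end of Section 3 refers the reader to these appendices for the full account of study procedures.

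The places that use the result name a different transporter gene. Objective 2.22 asks "whether there is an association of UGT1A1 (*28/*28) and SLC01B3 (rs2117032-C/T) with hyperbilirubinemia" (the gene is printed there with a zero for the letter O). Section 8.24 lists "SLCO1B3 (rs2117032-C/T) genotype" as a secondary response variable. Section 8.711 plans, if the data allow, a logistic model in which "SLCO1B3 (rs2117032-C/T) genotype, gestational age and gender as predictors will be fitted on the pooled data across the two cohorts". SAP Section 4.9 plans a table headed "Association between SLCO1B3 genotypes and hyperbilirubinemia (yes/no"), with the categories C/C, C/T and T/T.

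Section 1.27 also bears on the point. After naming UGT1A1 and SLCO1B3 (rs2117032), it says the "genetic variant will be evaluated at the end of the study".

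**The concern.** SLCO1B1 and SLCO1B3 are different genes. A paper cited in Section 1.27 lists both in its title, so a laboratory that received an order for SLCO1B1 would have no reason to suspect a slip. Section 3.2 gives raltegravir elimination as the reason for genotyping and does not mention hyperbilirubinemia, so nothing there would alert a reader that SLCO1B3 is needed.

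At stake is one secondary analysis. If typing follows only Section 3.2 and the footnotes, SAP Table 11 has no input, the SLCO1B3 predictor in the Section 8.711 model cannot be included, and the genotype that was obtained answers no stated question.

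**Working it through.** No sample size, rate or error probability is involved, so there is no figure of the plan's to reproduce. The check is a cross-reference of every mention of the two genes.

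**Where genotyping is ordered**
- Protocol 3.2: UGT1A1 and SLCO1B1
- Appendix II-A, footnote 11: UGT1A1 and SLCO1B1
- Appendix II-B, footnote 11: UGT1A1 and SLCO1B1

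Tally: SLCO1B1 in 3 of 3, SLCO1B3 in 0 of 3.

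**Where the result is used or its use is announced**
- Protocol Schema, secondary objective 2: SLCO1B3 (rs2117032-C/T)
- Protocol 1.27, statement of intent: SLCO1B3 (rs2117032)
- Protocol 2.22: SLCO1B3 (rs2117032-C/T)
- Protocol 8.24: SLCO1B3 (rs2117032-C/T)
- Protocol 8.711: SLCO1B3 (rs2117032-C/T)
- SAP Section 2, secondary objective 2: SLCO1B3 (rs2117032-C/T)
- SAP 4.9 and Table 11: SLCO1B3 (rs2117032-C/T)

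Tally: SLCO1B3 in 7 of 7, SLCO1B1 in 0 of 7. The only other mention of SLCO1B1 is in the title of the cited paper.

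**Has it been corrected?** The letter of amendment deals with maternal HIV documentation. Clarification Memorandum #1 deals with monitoring calls and the Cohort 1 consent form, and #2 with criterion 4.43. None touches genotyping.

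**How much of the objective is exposed?** Objective 2.22 has three components: UGT1A1 with raltegravir elimination, UGT1A1 with hyperbilirubinemia, and SLCO1B3 with hyperbilirubinemia. The gene name affects only the third: 1 of 3 components, or 1 of the 2 associations with hyperbilirubinemia.

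**How many infants?** SAP Section 2 gives final accrual under Version 1.0 as 10 + 6 + 26 = 42 pairs, and protocol Section 8.4 adds at least 8 infants in the Cohort 2 RAL-exposed group, so at least 50. This is only a pool from which genotyped infants could come. Genotyping is optional, and the documents do not say how many families agreed or which variants have been typed.

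**Does following the schedule destroy the information?** No. The site's task is to collect 250 to 400 µL of blood as a dried spot on filter paper, and that specimen is not specific to a gene. Collection, processing and shipping instructions are in the Laboratory Processing Chart, which is not among the documents.

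**The case against.** The strongest reply is that the intent is plain and the damage hypothetical. Section 1.27 names the right gene, the variant and the time of evaluation. SAP version 3.0, dated January 3, 2017, defines the SLCO1B3 categories and lays out the table, so the analysis team was working with the intended variant. Sites collect blood and do not choose assays. The two footnotes share their wording, so three occurrences may trace to one slip. The analysis is secondary: Section 8.711 allows that the model may not be feasible and expects minimal power, and the SAP calls the power of the Fisher test extremely limited.

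Much of this stands. Section 1.27 means that the protocol contradicts itself; it does not uniformly direct the wrong assay. The specimen point means that loss of data cannot be asserted. The low power keeps the matter away from any main conclusion.

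What does not follow is that the text can be left alone. Section 1.27 is background, whereas Section 3 makes the appendices the description of procedures. The SAP shows what the analysts expect to receive, not what the laboratory was told to type. It names a genotype data table as its source, but the documents do not show which variants that table holds. Little power is also not the same as no data.

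**Conclusion.** The contradiction is established and uncorrected in the documents supplied. Its consequence is conditional: if only the genes named in Section 3.2 and footnote 11 are typed, the SLCO1B3 component of objective 2.22 cannot be addressed. No primary endpoint, safety guideline or pharmacokinetic target depends on it.

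Stronger readings are tempting and are not supported:
- **That the genotype is already lost for all 42 accrued infants and those still to come.** This assumes that the laboratory typed SLCO1B1 alone and that no spots can be typed again. The documents show neither, and optional genotyping leaves the denominator unknown.
- **That half of the objective is lost.** It is one component of three.
- **That consent fails to cover SLCO1B3.** The consent pages are not available for this review, so their coverage is something to check, not a finding.
- **That SLCO1B1 is simply wrong.** The cited paper covers both genes, so the documents do not exclude SLCO1B1 as an additional marker. They only give it no analysis.

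**What to change.** Issue a clarification memorandum that names SLCO1B3 (rs2117032-C/T) in Section 3.2 and in footnote 11 of Appendices II-A and II-B. Keep SLCO1B1 there only if it is also intended; in that case, state its purpose in the protocol and add an analysis to SAP Section 4.9.

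Alongside the memorandum, confirm three things: that the Laboratory Processing Chart specifies rs2117032, that the genotyping consent covers it, and that stored spots from consenting families are typed for it before any are discarded.

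The cost is small. Clarification Memorandum #2 corrected a comparable wording error in criterion 4.43, and the sponsor did not require ethics approval before it took effect. No new blood is needed where usable spots remain. The cost would be higher only if the consent proved too narrow or spots had already been used up, and neither can be judged from these documents.
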